### 11.10.2. Seizures

SMQ: 'Convulsions' SMQ Code: 20000079 Category: A Scope: Narrow	
Preferred Term	PT Code
1p36 deletion syndrome	10082398
2-Hydroxyglutaric aciduria	10078971
Acquired epileptic aphasia	10052075
Acute encephalitis with refractory, repetitive partial seizures	10076948
Alcoholic seizure	10056347
Alpers disease	10083857
Aspartate-glutamate-transporter deficiency	10079140
Atonic seizures	10003628
Atypical benign partial epilepsy	10056699
Automatism epileptic	10003831
Autonomic seizure	10049612
Baltic myoclonic epilepsy	10054895
Benign familial neonatal convulsions	10067866
Benign rolandic epilepsy	10070530
Biotinidase deficiency	10071434
CEC syndrome	10083749
CDKL5 deficiency disorder	10083005
Change in seizure presentation	10075606
Clonic convulsion	10053398
Congenital bilateral perisylvian syndrome	10082716

Convulsion in childhood	10052391
Convulsions local	10010920
Convulsive threshold lowered	10010927
CSWS syndrome	10078827
Deja vu	10012177
Double cortex syndrome	10073490
Dreamy state	10013634
Drug withdrawal convulsions	10013752
Early infantile epileptic encephalopathy with burst-suppression	10071545
Eclampsia	10014129
Epilepsy	10015037
Epilepsy surgery	10079824
Epilepsy with myoclonic-ataxic seizures	10081179
Epileptic aura	10015049
Epileptic psychosis	10059232
Febrile convulsion	10016284
Febrile infection-related epilepsy syndrome	10079438
Focal dyscognitive seizures	10079424
Frontal lobe epilepsy	10049424
Gelastic seizure	10082918
Generalised onset non-motor seizure	10083376
Generalised tonic-clonic seizure	10018100
Glucose transporter type 1 deficiency syndrome	10078727
GM2 gangliosidosis	10083933
Grey matter heterotopia	10082084
Hemimegalencephaly	10078100
Hyperglycaemic seizure	10071394
Hypocalcaemic seizure	10072456

Hypoglycaemic seizure	10048803
Hyponatraemic seizure	10073183
Idiopathic generalised epilepsy	10071081
Infantile spasms	10021750
Juvenile myoclonic epilepsy	10071082
Lafora's myoclonic epilepsy	10054030
Lennox-Gastaut syndrome	10048816
Migraine-triggered seizure	10076676
Molybdenum cofactor deficiency	10069687
Multiple subpial transection	10079825
Myoclonic epilepsy	10054859
Myoclonic epilepsy and ragged-red fibres	10069825
Neonatal epileptic seizure	10082068
Neonatal seizure	10082067
Partial seizures	10061334
Partial seizures with secondary generalisation	10056209
Petit mal epilepsy	10034759
Polymicrogyria	10073489
Post stroke epilepsy	10076982
Post stroke seizure	10076981
Postictal headache	10052470
Postictal paralysis	10052469
Postictal psychosis	10070669
Postictal state	10048727
Post-traumatic epilepsy	10036312
Schizencephaly	10073487
Seizure	10039906
Seizure anoxic	10039907
Seizure cluster	10071350

Seizure like phenomena	10071048
Severe myoclonic epilepsy of infancy	10073677
Simple partial seizures	10040703
Status epilepticus	10041962
Sudden unexplained death in epilepsy	10063894
Temporal lobe epilepsy	10043209
Tonic clonic movements	10051171
Tonic convulsion	10043994
Tonic posturing	10075125
Topectomy	10073488
Transient epileptic amnesia	10081728
Tuberous sclerosis complex	10080584
Uncinate fits	10045476
Additional selected preferred terms from HLT "Disturbances in consciousness NEC" (Code: 10013509) under SOC "Nervous systems disorders" and HLT "Confusion and disorientation" (Code: 10010301) under SOC "Psychiatric disorders".	
Preferred Term	PT Code
Confusional state	10010305
Loss of consciousness	10024855
Syncope	10042772
Sopor	10058709
Stupor	10042264
Altered state of consciousness	10050093
Depressed level of consciousness	10012373
Consciousness fluctuating	10050093

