## **7.4. Adverse Events of Special Interest (AESIs)**

AESIs will be summarized for Hepatotoxicity and Seizures. QT Prolongation events will be listed. A comprehensive list of MedDRA terms based on clinical review will be used to identify each type of event for Adverse Events of Special Interest (AESI). [Changes to the MedDRA dictionary may occur between the start of the study and the time of reporting and/or emerging data from on-going studies may highlight additional adverse events of special interest, therefore the list of terms to be used for each event of interest and the specific events of interest will be based on the safety review team (SRT) agreements in place at the time of reporting.] The details of the current planned grouping, including Standardized MedDRA Query (SMQ) values (as applicable), and planned displays are provided in [Appendix 10: AESI Identification](#) and [Appendix 9: List of Data Displays](#).

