3.23.	Safety	201584/primary_07/ T3.134	Summary of Seizure Adverse Events of Special Interest by System Organ Class and Preferred Term (Number of Subjects and Occurrences)		SAC
3.24.	Safety	201584/primary_07/ T3.137	Summary of Hepatic Safety Profile: Assessment of Risk of Hepatotoxicity Adverse Events of Special Interest by System Organ Class and Preferred Term (Number of Subjects and Occurrences)		SAC
Laboratory: Chemistry					
3.25.	Safety	LB1	Summary of Chemistry Changes from Baseline by Study Phase and Visit	ICH E3	SAC
3.26.	Safety	LB1	Summary of Chemistry Values by Study Phase and Visit	ICH E3	SAC
3.27.	Safety	LB16	Summary of Chemistry Results by Maximum Grade Increase Post-Baseline Relative to Baseline	ICH E3 Repeat for each study phase	SAC
Laboratory: Hematology					
3.28.	Safety	LB1	Summary of Hematology Changes from Baseline by Study Phase and Visit	ICH E3	SAC
3.29.	Safety	LB1	Summary of Hematology Values by Study Phase and Visit	ICH E3	SAC
3.30.	Safety	LB16	Summary of Hematology Results by Maximum Grade Increase Post-Baseline Relative to Baseline	ICH E3 Repeat for each study phase	SAC

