## 11.10. Appendix 10: AESI Identification

SMQ and PT codes based on MedDRA dictionary version 23.0.

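### The seizure AESI list gives two different preferred terms the same PT code (10050093); if events are selected by code, at least one listed term cannot reach Table 3.23 (minor)

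*SAP*

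**What the plan says.** SAP 7.4 explains how AESIs are found: "A comprehensive list of MedDRA terms based on clinical review will be used to identify each type of event for Adverse Events of Special Interest". It refers to Appendix 10 for the groupings as currently planned. It adds that the terms finally used "will be based on the safety review team (SRT) agreements in place at the time of reporting".

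Appendix 10 (SAP 11.10) opens by stating its source: "SMQ and PT codes based on MedDRA dictionary version 23.0". Section 11.10.2 then sets out the seizure list in two blocks. The first is the narrow Convulsions SMQ. The second holds eight further preferred terms chosen from two high-level terms, one covering disturbances of consciousness and the other confusion and disorientation. Three consecutive rows of the second block read:

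- "Altered state of consciousness 10050093"
- "Depressed level of consciousness 10012373"
- "Consciousness fluctuating 10050093"

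The display that depends on this list is Table 3.23 in SAP 11.9.4, titled "Summary of Seizure Adverse Events of Special Interest by System Organ Class and Preferred Term (Number of Subjects and Occurrences"), run on the Safety population.

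**The concern.** A PT code is meant to identify a single preferred term. Here one code stands against two names, so at least one of the two rows is wrong as printed.

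This matters because the appendix specifies how events are selected. If a programmer filters adverse events on the printed codes, an event correctly coded to the term whose true code is absent will not be flagged as a seizure AESI. Drawing the SMQ afresh from the dictionary would not repair this, because both terms lie outside the SMQ.

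The protocol (2.3.1.1, Seizure) names seizure and seizure-like events as being of special interest for cabotegravir. Table 3.23 is the only planned display that groups them, and the SAP plans no separate seizure AESI listing. In a study that plans to inject about 15 participants, one omitted event could be the difference between a zero and a non-zero row in that table.

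**Working it through.** **Inputs.** All term and code rows in SAP 11.10.2: the Convulsions SMQ block and the block of additional terms.

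**Step 1: the SMQ block.** It has 90 rows and 90 distinct codes. No code repeats.

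**Step 2: the additional block.** It has 8 rows. In printed order the codes are 10010305, 10024855, 10042772, 10058709, 10042264, 10050093, 10012373, 10050093. That is 7 distinct codes. The repeated code, 10050093, belongs to the sixth row (*Altered state of consciousness*) and the eighth (*Consciousness fluctuating*).

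**Step 3: overlap between blocks.** None of the 7 additional codes occurs among the 90 SMQ codes.

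**Step 4: totals.**
- Terms: 90 + 8 = 98.
- Distinct codes: 90 + 7 = 97.
- Shortfall: 98 − 97 = 1.

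A filter on the printed codes can therefore cover at most 97 of the 98 listed terms. With a correct, distinct code on each row, the additional block would have 8 codes for 8 terms and the whole list 98 for 98.

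**Step 5: is it a table-reading fault?** The row between the two has its own code (10012373), and both names are printed in full on separate rows. A merged or shifted row would not readily produce this pattern.

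**Step 6: does the method of selection matter?**

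| Selection rule | Effect on Table 3.23 |
|---|---|
| By printed PT code | At least one listed term cannot be selected |
| By preferred term name | Both terms are captured; no effect |

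SAP 7.4 speaks of a list of terms and Appendix 10 describes itself by its codes. Neither states the matching rule.

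**Step 7: where would a missed event still be seen?** By preferred term in Table 3.3 (all adverse events by system organ class and preferred term), and in Listing 9 (all adverse events), Listing 10 (subject numbers for individual events) and Listing 31 (system organ class, preferred term and verbatim text).

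**Limit of the check.** The full count covers the seizure list only. Some codes recur across the two liver SMQs in 11.10.1, such as 10019772 for *Hepatitis fulminant*, but there the same term is listed twice under the same code, which is not this kind of error.

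**The case against.** The strongest reply is that the loss depends on a step the SAP does not prescribe. Section 7.4 identifies events from a list of terms, and both names are printed as separate rows, so matching on names captures both. That stands, and it makes the consequence conditional.

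A second reply is that the list may change: it follows the safety review team agreements in force at reporting, and the revision chronology marks this SAP as a critical-components version. That also stands, but only as an opportunity for correction. Nothing in the documents corrects the entry or calls for a check that codes are unique.

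A third is that the exposed term is peripheral. All 90 SMQ rows, including *Seizure*, *Epilepsy* and *Status epilepticus*, have their own codes. The protocol also requires seizure and seizure-like events to be reported within 24 hours, so case-level detection does not wait for Table 3.23. This is fair and keeps the point small.

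Three stronger readings are tempting, and the documents do not support them:

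- **That a missed event would be invisible in the report.** It would be absent from Table 3.23 only. Table 3.3 and Listings 9, 10 and 31 would still show it.
- **That each missed participant lowers the seizure AESI rate by 6.7 percentage points (1/15).** Fifteen is the approximate number to be injected. Table 3.23 uses the Safety population, which is everyone with at least one dose of study drug, so it also includes anyone who stops during the oral lead-in. A participant with another listed term would still be counted, and nothing in the documents gives an expected frequency for either term.
- **That the wrong row can be named.** The documents do not show which pairing is at fault, or what the missing code is.

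**Conclusion.** The duplicate is real and is the only code collision in the 98-row seizure list. At least one of the two pairings is wrong, on the assumption that a PT code identifies one preferred term, as it does in every other row of that list.

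The consequence is conditional. If selection is by the printed codes, at least one of the 98 terms cannot be selected, and any events coded to it would be missing from the only grouped seizure display. If selection is by term name, there is no effect. In either case the events remain in the general adverse event table and listings, and no primary pharmacokinetic endpoint is touched. The expected effect is small. Severity: minor.

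**What to change.** 1. Check *Altered state of consciousness* and *Consciousness fluctuating* against the MedDRA version in use, and correct whichever code in SAP 11.10.2 is wrong.
2. Before programming Table 3.23, run a check that each code in the seizure list maps to exactly one listed term.

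Do not require an event to match on both name and code. Such a rule drops events whenever the two disagree, and with the present error it would exclude a term that name matching captures.

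The cost is normally one corrected table cell and one short programming check. Design, conduct and sample size are unaffected.

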### 11.10.3. Torsade de pointes/QT prolongation

Notes: Medical concept of QT prolongation and complications. Only narrow terms from SMQ 'Torsade de pointes/QT prolongation' selected plus one additional PT under HLT 'ECG investigations'.

SMQ: Torsade de pointes/QT prolongation SMQ Code: 20000001 Category: A Scope: Narrow	
Preferred Term	PT Code
Electrocardiogram QT interval abnormal	10063748
Electrocardiogram QT prolonged	10014387
Long QT syndrome	10024803
Long QT syndrome congenital	10057926
Torsade de pointes	10044066
Ventricular tachycardia	10047302
Additional preferred terms selected from HLT 'ECG investigations' (Code: 10053104) under SOC 'Investigations'.	
Preferred Term	PT Code
Electrocardiogram repolarisation abnormality	10052464

#### 11.10.4. COVID-19 Adverse Events

COVID-19 adverse events are identified based on MedDRA coded values and/or AE referenced in the COVID-19 Coronavirus Infection assessment. The Lowest Level Terms (LLTs) and codes, Preferred Terms (PTs), High Level Terms (HLTs), High Level Group Terms (HLGTs), and System Organ Classes (SOCs), below are from MedDRA 23.0. In case there is a change to the version of MedDRA at time of reporting, the coded values based on the MedDRA version at the time of reporting will be used. The additional events may also be added based on the blinded review of AE data collected on study prior to the database freeze.

SOC: Infections and infestations

LLT code	LLT	PT	HLT	HLGT
10084459	Asymptomatic COVID-19	Asymptomatic COVID-19	Coronavirus infections	Viral infectious disorders

LLT code	LLT	PT	HLT	HLGT
10084467	Asymptomatic SARS-CoV-2 infection	Asymptomatic COVID-19	Coronavirus infections	Viral infectious disorders
10053983	Corona virus infection	Coronavirus infection	Coronavirus infections	Viral infectious disorders
10051905	Coronavirus infection	Coronavirus infection	Coronavirus infections	Viral infectious disorders
10084382	Coronavirus disease 2019	COVID-19	Coronavirus infections	Viral infectious disorders
10070255	Coronavirus test positive	Coronavirus test positive	Virus identification and serology	Microbiology and serology investigations

10084460	COVID-19 treatment	COVID-19 treatment	Antiinfective therapies	Therapeutic procedures and supportive care NEC
10084639	SARS-CoV-2 sepsis	SARS-CoV-2 sepsis	Coronavirus infections	Viral infectious disorders
10084271	SARS-CoV-2 test positive	SARS-CoV-2 test positive	Virus identification and serology	Microbiology and serology investigations
10084640	SARS CoV-2 viraemia	SARS CoV-2 viraemia	Coronavirus infections	Viral infectious disorders
10084268	COVID-19	COVID-19	Coronavirus infections	Viral infectious disorders
10084401	COVID-19 respiratory infection	COVID-19	Coronavirus infections	Viral infectious disorders
10084270	SARS-CoV-2 acute respiratory disease	COVID-19	Coronavirus infections	Viral infectious disorders
10084272	SARS-CoV-2 infection	COVID-19	Coronavirus infections	Viral infectious disorders
10084381	Coronavirus pneumonia	COVID-19 pneumonia	Coronavirus infections	Viral infectious disorders
10084380	COVID-19 pneumonia	COVID-19 pneumonia	Coronavirus infections	Viral infectious disorders
10084383	Novel COVID-19-infected pneumonia	COVID-19 pneumonia	Coronavirus infections	Viral infectious disorders
10084451	Suspected COVID-19	Suspected COVID-19	Coronavirus infections	Viral infectious disorders
10084452	Suspected SARS-CoV-2 infection	Suspected COVID-19	Coronavirus infections	Viral infectious disorders
10084461	SARS-CoV-2 carrier	SARS-CoV-2 carrier	Infectious disorders carrier	Ancillary infectious topics
